5.1. Inclusion Criteria

All the following inclusion criteria must be met for a participant to be eligible for this study:

1. Provide a signed and dated informed consent form (ICF).
2. Chinese male or female with age ≥ 18 years old at the time of the informed consent.
3. Documented histology- and/or cytology-confirmed metastatic melanoma or NSCLC (i.e. adenocarcinoma, large cell carcinoma, squamous cell carcinoma).
4. Presence of *BRAF* V600E mutation as determined by a local laboratory with a NMPA approved *BRAF* test.
5. *BRAF* inhibitor treatment-naïve participants and having failed the previous therapy(ies) for metastatic disease or are not eligible to standard therapy.

Note:

Alternative chemotherapy regimen is permitted if participants were platinum intolerant or ineligible.

6. At least one tumor lesion as per investigator assessment according to RECIST Version 1.1, which has neither been irradiated nor biopsied during the screening period. The irradiated lesion is acceptable only if it is proven as disease progression deemed measurable prior to study.
7. Life expectancy ≥ 3 months.
8. ECOG performance status of 0 or 1.
9. Adequate hematologic function at screening and baseline characterized by the following:
 - a. *Absolute neutrophil count $\geq 1.5 \times 10^9/L$.*
 - b. *Hemoglobin ≥ 90 g/L.*
 - c. *Platelets $\geq 100 \times 10^9/L$.*

d. *International normalized ratio, prothrombin time or (activated) partial thromboplastin time $\leq 1.5 \times$ upper limit of normal (ULN).*

10. Adequate hepatic function at screening and baseline characterized by the following:

- Total bilirubin $\leq 1.5 \times$ ULN.*
Note: Total bilirubin $> 1.5 \times$ ULN is allowed if indirect bilirubin is $\leq 1.5 \times$ ULN.
- Alanine aminotransferase and aspartate aminotransferase $\leq 2.5 \times$ ULN or $\leq 5 \times$ ULN in case of documented liver metastases.*

11. Adequate renal function at screening and baseline characterized by the following:

- Serum creatinine $\leq 1.5 \times$ ULN.*
- Creatinine clearance ≥ 50 mL/min as calculated by the Cockcroft-Gault formula; or estimated glomerular filtration rate > 50 mL/min/1.72m².*

12. Able to comply with the study protocol as per investigator assessment including oral drug intake, complying scheduled visits, treatment plan, laboratory tests and other study procedures.

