6.6. Dose Modification

Participants will be monitored for adverse events throughout the study. The severity of adverse events will be graded according to National Cancer Institute Common Terminology Criteria for Adverse Events NCI CTCAE Version 4.03 [NCI CTCAE 2010].

If a participant develops toxicity, the dose should be modified as outlined in Appendix 10.4. This table include criteria for interruption, reduction and discontinuation of study treatment. All dose modifications should be based on the worst preceding toxicity. All dosing interruptions and modifications must be recorded in the eCRF.

Individual decisions regarding dose modifications should be made using appropriate clinical judgment, considering relatedness of the adverse event to the study treatment and the participant's underlying condition. Adverse events that have a clear alternative explanation or are transient (≤ 72 hours) abnormal laboratory values without associated clinically significant signs or symptoms may be exempt from dose reduction rules. The investigator should follow the study site supportive guidelines for the management of these toxicities and prophylactic measures.

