9.1. Statistical Hypotheses

Because of the exploratory nature of the study, all data will be analyzed descriptively and not with an inferential approach. No formal statistical testing will therefore be performed.

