10.4. Appendix 4: Dose Modifications for Encorafenib-related Adverse Events

Table 19: Recommended Dose Modifications for Encorafenib-related Adverse Events

Worst Toxicity NCI CTCAE Version 4.03 Grade (unless otherwise specified)	Dose Modification for Encorafenib
Eye disorders - Posterior uveitis (including iritis and iridocyclitis)	
Any visual acuity impairment at screening should be documented and should be considered as baseline.	
Grade 1 or 2	
Treat with specific (e.g. topical) ocular therapy. If uveitis does not respond, interrupt dosing of encorafenib and repeat ophthalmic monitoring including visual acuity assessment within 10 days.
 
If resolved to baseline or \leqGrade 1 resume study treatment at the same dose.
 
If posterior uveitis lasts >6 weeks, permanently discontinue encorafenib.

Grade 2	
Treat with specific (e.g. topical) ocular therapy. If uveitis does not respond, interrupt dosing of encorafenib and repeat ophthalmic monitoring including visual acuity assessment within 10 days.
 
If resolved to \leqGrade 1, resume study treatment at one reduced dose level of encorafenib[a].
 
If posterior uveitis lasts >6 weeks, permanently discontinue encorafenib and ophthalmic monitoring should be repeated.

Grade 3	
Interrupt dosing of encorafenib and repeat ophthalmic monitoring including visual acuity assessment within 10 days.
 
If resolved to \leqGrade 1, resume study treatment at one reduced dose level of encorafenib[a].
 
If posterior uveitis lasts >6 weeks, permanently discontinue encorafenib and ophthalmic monitoring should be repeated.

Grade 4	Permanently discontinue encorafenib and immediately follow-up with ophthalmic monitoring[b]
Liver-related adverse events	
Grade 1 AST or ALT $>ULN$ to $3 \times ULN$	Maintain dose level of encorafenib.
Grade 2 AST or ALT >3 to $5.0 \times ULN$ or $3 \times$ baseline value[c] AND blood total bilirubin $\leq 2.0 \times ULN$	
Maintain dose level of encorafenib.
 
If not resolved in ≤ 14 days, interrupt dose of encorafenib until resolved to Grade ≤ 1 (or Grade ≤ 2 in case of liver metastasis), then resume study treatment at current dose level of encorafenib.
 
If additional occurrence:
 
Interrupt dosing of encorafenib until resolved to Grade ≤ 1 (or Grade ≤ 2 in case of liver metastasis), then resume study treatment at one reduced dose level[a] of encorafenib.

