	
[b] Ophthalmic monitoring mandated for posterior uveitis: further evaluation with specialized retinal imaging in addition to basic assessment (e.g. best corrected visual acuity testing, slit lamp examination, intraocular pressure and dilated fundoscopy). Any diagnosis of retinal events must be supported by presence or absence of symptoms and visual acuity assessment as well as any other document findings.[c] For participants enrolled with liver metastases and baseline liver function test elevations.[d] Disorder characterized by redness, marked discomfort, swelling and tingling in the palms of the hands or the soles of the feet.[e] A participant with a Grade 4 adverse event may resume encorafenib at the lower dose level if the event recovers to Grade ≤ 1 within 28 days of discontinuing study treatment and, if in the opinion of the investigator and medical monitor, the event is not life-threatening and the participant can be managed and monitored for recurrence of the event. Any participants requiring a dose interruption of duration >28 days must discontinue encorafenib permanently.

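### For participants with liver metastases, Table 19's Grade 2 AST/ALT rule orders an interruption whose restart condition is already met at >3 to 5.0 × ULN

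*Protocol*

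**What the plan says.** The rule is in Protocol Appendix 4 (Section 10.4), Table 19, under liver-related adverse events. The Grade 2 row is entered at AST or ALT >3 to 5.0 × ULN, or at 3 × "baseline value[c] AND blood total bilirubin" ≤2.0 × ULN. Footnote [c] limits the second route: "For participants enrolled with liver metastases and baseline liver function test elevations".

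The row gives two instructions:

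- **First occurrence.** Keep the dose. If the event has not resolved within 14 days, interrupt until Grade ≤1, or Grade ≤2 "in case of liver metastasis), then resume study treatment at current dose level of encorafenib".
- **Additional occurrence.** Interrupt until Grade ≤1, or Grade ≤2 "in case of liver metastasis), then resume study treatment at one reduced dose level[a] of encorafenib".

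The Grade 3 row (>5.0 to 8.0 × ULN, same bilirubin limit) carries the same bracket for liver metastasis.

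The affected population is expressly admitted. Inclusion criterion 10 allows ALT and AST up to 5 × ULN "in case of documented liver metastases". Section 6.6 adds: "All dose modifications should be based on the worst preceding toxicity".

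Protocol Section 7.1.1 counts a treatment interruption only when at least one administration is missed and dosing then restarts. SAP Section 5.6.1 identifies a dose interruption by a 0 mg dosing record for one or more days.

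**The concern.** In the Grade 2 row the liver-metastasis restart threshold is the same grade as the event that opens the row. Under Section 7.1.1 an interruption needs a missed dose, yet the stated end condition is true before any dose has been missed. A site cannot act fully on both halves of the sentence.

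One site may hold drug until some improvement is seen. Another may see that Grade ≤2 is satisfied and dose without a gap. The same laboratory course would then give different exposure and a different entry in the interruption tables. TEAEs leading to dose interruption or reduction are a secondary endpoint and one of the items the Trial Steering Committee weighs for tolerability, in a study of three to six evaluable participants.

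**Working it through.** No sample size, power or alpha figure is involved (Protocol Section 9.1: "No formal statistical testing will therefore be performed"). The check is logical, with some day-counting for the consequences.

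**1. Grade limits from Table 19.** Grade 1 is >ULN to 3 × ULN, Grade 2 is >3 to 5.0, the Grade 3 row is >5.0 to 8.0, a separate row covers >8, and Grade 4 is >20.

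**2. ULN route into the Grade 2 row.** The values 3.01, 3.5, 4, 4.5 and 5.0 × ULN are all Grade 2. Each fails Grade ≤1 and each meets Grade ≤2. Without liver metastases the rule works. With them, the restart condition holds across the whole range.

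**3. Same bracket in the Grade 3 row.** Entry is >5.0 × ULN and exit at Grade ≤2 is ≤5.0 × ULN. The two do not overlap, so the bracket is coherent there.

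**4. The 3 × baseline route.** The value at the trigger is 3 × baseline, and it exceeds 5 × ULN when baseline exceeds 5/3 ≈ 1.67 × ULN.

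| Baseline (× ULN) | 3 × baseline (× ULN) | Already Grade ≤2? | Row the absolute value falls in |
|---|---|---|---|
| 1.1 | 3.3 | Yes | Grade 2 |
| 1.5 | 4.5 | Yes | Grade 2 |
| 1.67 (5/3) | 5.0 | Yes | Grade 2 |
| 2 | 6 | No | >5.0 to 8.0 |
| 2.5 | 7.5 | No | >5.0 to 8.0 |
| 3 | 9 | No | >8 |
| 5 (entry limit) | 15 | No | >8 |

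Above 1.67 × ULN, Grade ≤2 is a real condition. But the same value then belongs to the Grade 2 row by its multiple of baseline and to a higher row by its multiple of ULN, and those rows prescribe different actions.

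**5. The 14-day test.** The row does not define *resolved*. If it means Grade ≤2 for liver metastasis, an event in the >3 to 5.0 × ULN range never triggers the interruption. If it means Grade ≤1, the interruption is triggered and its end condition is met at once.

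**6. Reach into Cycle 1 evaluability.**

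- The planned Cycle 1 dose is 28 × 300 = 8400 mg (SAP Section 5.6.1). The 75% requirement is 0.75 × 8400 = 6300 mg, or 21 doses, so more than 7 doses must be missed.
- An interruption starting on Day 21 misses Days 21 to 28, which is 8 doses. The event must therefore be found by about Day 21 − 14 = Day 7.
- After baseline, scheduled chemistry is on Day 15 and then Cycle 2 Day 1 (Protocol Section 8.3.4). Day 15 + 14 = Day 29, which is already Cycle 2.
- With the 48-hour early-sampling allowance, Day 13 + 14 = Day 27, so at most 2 doses are missed.
- An additional occurrence by Day 15 needs a first one already found and resolved, again by unscheduled testing.

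**7. Reach into the counts.** SAP Section 5.6.2 tabulates TEAEs leading to interruption, to reduction, and to either.

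- First occurrence: holding the drug adds an interruption, and dosing through adds nothing, so the separate and combined counts both differ.
- Additional occurrence: the reduction applies either way, so the combined count is the same and only the separate interruption count differs.

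**8. Reach into the primary endpoint.** Every transaminase criterion in Protocol Table 4 needs Grade 3 or higher, so a Grade 2 event is not a DLT under either reading.

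**The case against.** The strongest reply is that the row has two entry routes, and the second is reserved for part of the very group at issue. A reader might infer that every value opening the row already satisfies the restart condition. That is too broad: by the 3 × baseline route with baseline above about 1.67 × ULN, it does not. This part of the objection stands and limits the point to the >3 to 5.0 × ULN range. It does not rescue the rule there, because the bracket applies to liver metastasis in general, not only to footnote [c] participants, and the excepted values fall into the higher rows as well.

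A second reply is that Table 19 is headed as recommended modifications and Section 6.6 leaves individual decisions to clinical judgment. That softens the practical effect, but it does not tell a site whether the order to interrupt or the Grade ≤2 condition prevails.

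A third reply is that leniency for liver metastases was intended. If so, the order to interrupt has no function; if a hold was intended, the restart condition defeats it. The documents do not say which, so it cannot be asserted that the row strips these participants of an intended protection. Either intention needs an edit.

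**Conclusion.** The point holds in limited form. For participants with liver metastases and AST or ALT of >3 to 5.0 × ULN, both instructions in the Grade 2 row pair an interruption with an end condition that is already met. In the additional-occurrence instruction only the dose step-down has an effect. This assumes grading by Table 19's own ULN limits; no other text in either document gives the bracket another meaning.

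The consequence is inconsistent handling between sites, with an effect on exposure and on the separately tabulated interruption counts. Its size cannot be estimated, because neither document gives a rate of liver metastases or of persistent Grade 2 elevations.

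Three stronger inferences are not supported:

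- **A general threat to Cycle 1 evaluability.** On scheduled chemistry the first-occurrence rule cannot cost the more than 7 doses required; an early unscheduled test is needed.
- **An effect on the DLT rate or the <33% criterion.** No transaminase DLT can arise from a Grade 2 event.
- **A fixed share of the sample.** One participant is 1/6 = 17% to 1/3 = 33% of six or three, but that is true of any single participant and does not measure this defect.

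**What to change.** In Table 19's Grade 2 AST/ALT row, reconcile three elements for participants with liver metastases: the interruption trigger, the meaning of *resolved* in the 14-day test, and the restart condition. Do this in both the first-occurrence and the additional-occurrence instruction, so that the end condition is not already true when the interruption starts. Also state which row governs when a value reached by the 3 × baseline route exceeds 5 × ULN. The sponsor's clinical team decides the thresholds; no value is proposed here.

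The cost is a wording change to one table row and, if needed, footnote [c], made by protocol clarification or amendment and notified to the two or three sites. The sample size, the DLT definition and the SAP tables stay as they are.

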Overall Design:	
This is a phase 1, multicenter, open-label, single-arm study to investigate the safety and tolerability of encorafenib 300 mg once daily (QD) monotherapy in adult Chinese participants with BRAF V600E mutant advanced solid tumors (unresectable metastatic melanoma or metastatic NSCLC), who are BRAF-inhibitor treatment-naïve and have failed the previous therapy(ies) for advanced metastatic disease or are not eligible to standard therapy. Participants will be eligible for the study based on identification of a BRAF V600E mutation in tumor tissue by a local National Medical Products Administration (NMPA) approved assay obtained prior to screening.
 
A dose limiting toxicity (DLT) is defined as any adverse event or abnormal laboratory value assessed as unrelated to disease, disease progression, intercurrent illness or concomitant medications/therapies resulting in the inability to tolerate at least 75% dose

	
intensity [(administered dose in mg/planned dose in mg) × 100] occurring within the first 28 days of study treatment (Cycle 1) that satisfies at least one of the predefined DLT criteria.
 
It is planned to enrol up to six evaluable participants using a 3+3 design. To be evaluable for tolerability assessment, participants must have either experienced an event meeting the DLT criteria in Cycle 1 or completed at least one cycle of study treatment and received at least 75% of the encorafenib dose intensity in Cycle 1. Non-evaluable participants, including withdrawals during Cycle 1 for reasons other than a DLT, will be replaced.
 
 • Three participants will initially be enrolled and receive encorafenib 300 mg QD, and will be evaluated for DLTs during the first cycle of treatment (28 days) [the DLT evaluation period]: 
 – If there are no DLTs in the first three participants in the DLT evaluation period, enrollment will be stopped. – If one of the first three participants experiences a DLT in the DLT evaluation period, a Trial Steering Committee (TSC) will make the recommendation whether three additional participants will be enrolled to expand the number of participants to a total of six. – If more than one of the first three treated participants experience a DLT, enrollment will be stopped. • If the group is expanded and two or more of the six participants experience a DLT, enrollment will be stopped.

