		Grade 4 ALT or AST
		≥Grade 3 ALT or AST and ≥Grade 2 blood bilirubin
Investigations (metabolic)		Grade 3 lipase for >7 consecutive days
		Grade 4 lipase
Cardiac disorders		≥Grade 3
Gastrointestinal disorders		≥Grade 3 vomiting or nausea lasting more than 48 hours despite optimal antiemetic therapy[b]
		≥Grade 3 diarrhea lasting more than 48 hours despite optimal treatment
		≥Grade 3 pancreatitis
Skin and subcutaneous tissue disorders[c]: rash, photosensitivity or HFSR		Grade 3 rash/photosensitivity/HFSR for >7 consecutive days despite skin toxicity treatment (as per local practice)
		Grade 4 rash/photosensitivity/HFSR
General disorders and administration site conditions		Grade 3 fatigue/asthenia for >7 consecutive days
Ophthalmologic	Uveitis	Grade 3 for >21 consecutive days confirmed by ophthalmologic examination

Toxicity		Any of the following criteria
		Grade 4 confirmed by ophthalmologic examination
Any other eye disorders	Grade 3 for >21 consecutive days	
	Grade 4	
Other adverse events[d]		≥Grade 3 adverse events (excluding SCC)

Abbreviations: ALT = alanine aminotransferase; ANC = absolute neutrophil count; AST = aspartate aminotransferase; DLT = limiting dose toxicity; HFSR = hand-foot skin reaction (also known as palmar-plantar erythrodysesthesia [PPE] syndrome); NCI CTCAE = National Cancer Institute Common Terminology Criteria for Adverse Events; ULN = Upper limit of normal.

Grades according to NCI CTCAE grading system.

- [a] ≥Grade 3 anemia will not be considered a DLT unless judged to be a hemolytic process secondary to study treatment. ≥Grade 3 lymphopenia will not to be considered a DLT unless clinically significant.
- [b] Optimal therapy for vomiting or diarrhea will be based on study site guidelines with consideration of the prohibited medications listed in this protocol.
- [c] Squamous cell carcinoma reported to be an on-target side-effect that was manageable will not be considered a DLT.
- [d] An adverse event must be clinically significant to be defined as a DLT: alopecia, study treatment-related fever, electrolyte abnormalities (including K, NA, Cl, HCO₃, Mg, Ca, PO₄) that are ≤Grade 3 abnormalities will not be considered a DLT unless clinically significant.

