7.1.2. Permanent Study Treatment Discontinuation

Study treatment is to be administered until any of the following criteria for permanent discontinuation is met:

- Disease progression, as defined by Response Evaluation Criteria in Solid Tumors (RECIST) Version 1.1 (continuation of treatment beyond progression is permitted in special circumstances, see **Section 6.1**).

- Clinical progression, as determined by the investigator in the absence of radiographic progression.
- Withdrawal of consent. Participants may choose to withdraw consent to continue study treatment but remain in the study to be followed for safety and disease progression. In this case, follow-up data will continue to be collected for this participant. Withdrawal of consent for study treatment may occur at any time without penalty of jeopardizing their healthcare or loss of benefits to which they are otherwise entitled. Participants who withdraw consent to study treatment and follow-up, will no longer receive study treatment or followed up within this study.
- Unacceptable adverse events or failure to tolerate study treatment:
 - Grade 4 or life-threatening adverse event as outlined in Appendix 10.4 (except with approval from the sponsor's medical monitor)
 - Toxicity requiring more than the allowed number of dose reductions for encorafenib, (see **Table 7**).
 - Occurrence of an adverse event that is related to study treatment and compromises the participant's ability to continue study-specific procedures according to investigator's judgement or is considered to not be in the participant's best interest. The medical monitor or delegate should immediately be informed by phone or e-mail and a report explaining the discontinuation will be forwarded to him/her as soon as possible.
- Initiation of subsequent anticancer therapy.
- Participant is non-compliant with study procedures or study treatment that in the judgment of the investigator or sponsor renders the participant unsuitable.
- Significant protocol deviation that, in the opinion of the investigator and/or sponsor, renders the participant unsuitable for further study treatment administration.
- Participant has missed >4 weeks (i.e., 28 consecutive days) of dosing (see Section 7.1.1).
- Participant becomes pregnant or begins breastfeeding.
- Participant is lost to follow-up.
- Defined end of the study (see Section 4.4)

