Grade 3 or 4	Interrupt dosing of encorafenib until resolved to Grade ≤ 1 . Then resume treatment at current dose level of encorafenib if, in the judgment of the investigator, the toxicity is considered to be unrelated to encorafenib, or at one reduced dose level[a].
Nausea/vomiting	
Grade 1 or 2	Maintain dose level of encorafenib. Promptly institute antiemetic measure.
Grade 3	Interrupt dosing of encorafenib until resolved to Grade ≤ 1 . Then resume treatment at one reduced dose level[a] of encorafenib. Note: Interrupt dosing of encorafenib for \geq Grade 3 vomiting or Grade 3 nausea only if the vomiting or nausea cannot be controlled with optimal antiemetics (based on study site standards).
Grade 4	Permanently discontinue encorafenib[e].
All other adverse events (suspected to be related to encorafenib)	
Grade 1 or 2	If the event is a persistent Grade 2 adverse event not responsive to a specific therapy, consider interruption or reduction of encorafenib, as applicable
Grade 3	Interrupt dosing of encorafenib until resolved to Grade ≤ 1 or to pretreatment/baseline level. If the event resolves ≤ 21 days, then encorafenib may be resumed at one reduced dose level[a] based upon the investigator's discretion.
Grade 4	Permanently discontinue encorafenib[e].

Abbreviations: ALT = alanine aminotransferase; AST = aspartate aminotransferase; CK = creatine kinase; HFSR = hand-foot skin reaction; KA = keratoacanthoma; NCI CTCAE = National Cancer Institute Common Terminology Criteria for Adverse Events; PPE = Palmar-plantar erythrodysesthesia; QTcF = QT interval corrected for heart rate using Fridericia's formula; SCC = squamous cell carcinoma; ULN = upper limit of normal.
 
[a] Dose reduction below 150 mg QD is not allowed.
	

Worst Toxicity NCI CTCAE Version 4.03 Grade (unless otherwise specified)	Dose Modification for Encorafenib

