In addition, the RDI specific to Cycle 1 will be defined as 100*administered dose (mg) through Cycle 1 divided by planned dose (mg), with planned dose being 8400 mg for encorafenib (28 daily doses of 300 mg).

Relative dose intensity in Cycle 1 will be listed in the listing of dose intensities.

Dose modifications will be defined as below:

- A dose interruption will be indicated in the eCRF by a dosing record with a total daily dose of 0 mg for one or more days.

To avoid over-counting interruptions, dosing records with 0 mg entered as last dosing record will not be counted as interruptions. Those represent the reason for permanent discontinuation and will therefore be presented in the reason for treatment permanent discontinuation analysis.

- A dose reduction is defined as a decrease in dose from the protocol-planned dose and a decrease from the previous non-zero dose, even if this decrease has been directly preceded by an interruption. For example, for encorafenib, in the sequence of total daily dose 300 mg – 0 mg – 200 mg, the 200 mg dose will be counted as a reduction.

If a participant moves from a higher than protocol-planned dose down to the planned dose then this is not to be counted as a reduction, however if they move directly from a higher than planned dose down to a lower than protocol-planned dose or the planned dose on a less frequent regimen, then this is counted as a reduction.

If the dose on the first dosing record is lower than protocol-planned dose this is also counted as a reduction.

Frequency counts and percentages of participants who have dose reductions or interruptions, and corresponding reasons, will be summarized for participants from the SAF. Dose reductions and interruptions will be tabulated both separately and in a combined fashion.

Sponsor Name: Pierre Fabre Médicament

Sponsor Protocol ID: W00090GE102

PII

For participants with dose reduction as defined above, the percentages of days between the first and last non-zero dose with reduced dose i.e., below the protocol-planned dose will be summarized and specified in the related listing. Note, in this calculation a dose of 0 mg will also be considered a reduced dose.

For participants with dose interruption as defined above, the percentages of days with dose interruption will also be summarized and specified in the related listing.

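### The antiemetic note in Table 19 covers vomiting of Grade 3 or higher, so read literally it lets dosing continue through controlled Grade 4 vomiting, against the Grade 4 row

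*Protocol*

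**What the plan says.** Protocol Appendix 4 (Section 10.4), Table 19, handles nausea and vomiting by grade.

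- **Grade 3 row.** Interrupt until Grade 1 or lower, then resume one dose level down. A note in the same cell limits the interruption. Immediately after a ≥ sign it reads "Grade 3 vomiting or Grade 3 nausea only if the vomiting or nausea cannot be controlled with optimal antiemetics". The sign applies to vomiting; nausea is given as Grade 3 alone.
- **Grade 4 row.** Discontinue permanently, with a pointer to footnote [e] and no condition about antiemetics.
- **Footnote [e].** "A participant with a Grade 4 adverse event may resume encorafenib at the lower dose level", provided it recovers to Grade 1 or lower within 28 days and the investigator and medical monitor agree that it is not life-threatening and can be managed.

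Two body sections bear on this. Section 6.6 says "All dose modifications should be based on the worst preceding toxicity". Section 7.1.2 makes a Grade 4 event, as set out in Appendix 10.4, a reason for permanent discontinuation unless the sponsor's medical monitor approves otherwise.

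For the primary endpoint, the vomiting criterion in Table 4 (Section 4.1.1) is Grade 3 or higher, with the duration condition "Grade 3 vomiting or nausea lasting more than 48 hours despite optimal antiemetic therapy". A participant without a DLT is evaluable only after completing Cycle 1 with at least 75% dose intensity. The Synopsis says that non-evaluable participants, "including withdrawals during Cycle 1 for reasons other than a DLT, will be replaced".

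**The concern.** Table 19 is the table an investigator uses to decide whether to stop the drug. Read literally, its note withholds interruption for Grade 4 vomiting as long as antiemetics work, while the row beneath withdraws the drug. One site could keep a participant on 300 mg and another could stop. The note's reading is the less protective one, and it avoids the medical monitor's involvement that both footnote [e] and Section 7.1.2 require.

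There is a secondary effect on the DLT assessment. Vomiting brought under control within 48 hours does not meet the vomiting criterion in Table 4. If the event falls in Cycle 1, the instruction followed can then decide whether the participant counts as evaluable without a DLT or is replaced. The initial cohort has three participants, and no DLTs among them ends enrollment, so one participant is a third of the evidence.

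**Working it through.** **Instructions side by side for Grade 4 vomiting**

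| Situation | Note in the Grade 3 row | Grade 4 row |
|---|---|---|
| Controlled by antiemetics | No interruption | Permanent stop; footnote [e] may allow a restart |
| Not controlled | Interrupt | Permanent stop; footnote [e] may allow a restart |

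In the uncontrolled case both instructions stop dosing, at least for a time, so they are much closer. The sharp conflict is in the controlled case. Grade 4 nausea is not affected, because the note names only Grade 3 nausea.

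**Does other text settle it?**

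- Section 7.1.2 defers to Appendix 10.4, which is where the conflict sits.
- Footnote [e] governs restarting at a lower dose after a stop. It does not authorise uninterrupted 300 mg.
- Section 6.6 fixes the grade to be used. It does not rank two instructions that both cover Grade 4.
- The diarrhea rows of the same table handle Grades 3 and 4 together, by interruption and resumption. A site therefore cannot assume that Grade 4 always means a permanent stop.

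**Effect on Cycle 1 evaluability**

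Inputs: 300 mg daily for 28 days (SAP Section 5.6.1, "with planned dose being 8400 mg for encorafenib"); the 75% threshold (Protocol Sections 4.1.1 and 9.3); first reduced level 225 mg (Protocol Table 7). The example is my assumption: Grade 4 vomiting on Day 8, after that day's dose, controlled within 48 hours.

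Dose intensity = administered mg / planned mg.

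- Planned dose: 28 × 300 = 8400 mg. Threshold: 0.75 × 8400 = 6300 mg, and 6300/300 = 21 full doses.
- Given through Day 8: 8 × 300 = 2400 mg.

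| Handling | Administered dose | Dose intensity | 75% met? |
|---|---|---|---|
| Note followed, no dose missed | 28 × 300 = 8400 mg | 8400/8400 = 100% | Yes |
| Grade 4 row, permanent stop | 2400 mg | 2400/8400 = 28.6% | No |
| Footnote [e], 2 days off, then 18 days at 225 mg | 2400 + 4050 = 6450 mg | 6450/8400 = 76.8% | Yes |
| Footnote [e], 3 days off, then 17 days at 225 mg | 2400 + 3825 = 6225 mg | 6225/8400 = 74.1% | No |

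Any permanent stop before the 21st full dose leaves the participant below 75%: 20 doses give 6000/8400 = 71.4%.

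**The case against.** The best reply is that the table is entered by worst grade. Grade 4 vomiting leads to the Grade 4 row, and a note inside the Grade 3 cell qualifies only that cell. The note speaks of interruption; it never says to maintain dosing at Grade 4. Section 7.1.2 requires the medical monitor's approval before treatment continues after such an event. The introduction to Section 8 sends immediate safety concerns to the sponsor to decide on continuation, and Section 8.4.2 requires serious events to be reported within 24 hours. With two or three sites and at most six evaluable participants, unnoticed divergence is unlikely.

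This establishes the probable intent, and it makes prolonged divergence less likely. It does not remove the conflict. A note confined to Grade 3 has no use for a ≥ sign, and because the same sentence uses the sign for vomiting but not for nausea, a reader has reason to think it deliberate.

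The reply is stronger on evaluability. Replacement after an early stop comes from the 48-hour condition, the 75% rule and the replacement rule, not from the note. Correcting the note leaves the stop, with footnote [e], as the only route, so replacement can still follow. The event is not lost either: the participant stays in the Safety Set, and the Trial Steering Committee reviews overall toxicity. If the event were classed under Table 4's row for other adverse events, the participant would be evaluable with a DLT on either reading and this effect would disappear. The dosing conflict would remain.

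**Conclusion.** The concern holds as a wording error in an operative safety table. It is confined to Grade 4 vomiting that antiemetics control, and the Grade 4 row is the likely intent. The practical effect is small, on the assumption that such events are rare.

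The DLT criteria, the <33% rule and the sample size are untouched. The evaluability effect is a difference between readings, not a bias of known size. It arises only for an event in Cycle 1 that is controlled within 48 hours and is not counted as a DLT under another row, and the percentages depend on the Day 8 example and the chosen gaps in dosing. The correction is still worth making, because the literal reading is the less protective one and the change is trivial.

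**What to change.** In Protocol Appendix 4, Table 19, delete the ≥ sign before Grade 3 vomiting in the note to the Grade 3 nausea/vomiting row. The note then covers Grade 3 vomiting and Grade 3 nausea only, and Grade 4 vomiting is governed solely by the Grade 4 row with footnote [e] and Section 7.1.2.

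The cost is one symbol in one table cell of the protocol. The DLT criteria, the sample size and the SAP stay as they are.
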